8.3 Study Duration

8.3.1 Approximate Duration of Subject Participation

We expect subjects will participate in the study for up to 24 months. Currently, participants do not graduate from the program, but this may change as the program evolves.

8.3.2 Approximate Duration of Study

This study will be completed in three years, defined as the last period when electronic medical records will be consulted for utilization outcomes.

[figure not shown]
We expect the effects of the program will be detectable at 6 months, with some convergence at 12 months as the control group enters the program and begins treatment; we expect the treatment group to still exhibit benefits relative to the control group at 12 months given that they will have participated in the program for twice as long and had more time to change their dietary habits and for the effects of such changes to be felt. Utilization, such as ED usage, may be noticed in this later period.

8.4 Procedures

Baseline biometric measures (HbA1c, fasting glucose, weight, BMI, blood pressure and lipid panel) will be collected utilizing the most recent values available in the subjects' medical records within the year prior to enrolling in the FFF study. These biometric measures will be used to determine eligibility for the study and during data analysis.

A set of blood tests (HbA1c, fasting glucose and lipid panel) will be collected for research immediately prior to the subject beginning the FFF program (month 0 for treatment group or approximately month 6 for the control group). In addition, research participants will complete a baseline survey upon entry into the FFF program. This survey will be completed on site at the FFF program clinic.

A set of research biometric measurements (HbA1c, fasting glucose, weight, BMI, blood pressure and lipid panel) will be collected at approximately the 6 and 12 month time points (plus or minus

1 month) for the treatment group. A set of research biometric measurements (HbA1c, fasting glucose, weight, BMI, blood pressure and lipid panel will be collected at approximately the 12 month time point (plus or minus 1 month) for the control group.

In addition, all research participants will complete a survey after 6- and 12-months of participation (similar to the baseline survey) during FFF program visits. For those who do not enroll in the study, we will not continue to investigate their outcomes at these intervals.

Protocol required lab draws will be paid for by the study. Patients will be compensated with a \$50 gift card for the time and effort to complete the lab work and the patient surveys.

Based on our experience with the FFF program, we expect nearly all the patients to continue with the study. For the few who do drop out of the study but remain in the program, we will contact these subjects and collect outcome information, including clinical lab results and the ongoing survey. For those who drop out of the FFF program, but remain in the study the lab work will be covered by the research study and the surveys will be completed by phone or e-mail. The patients will be offered a \$50 gift card as compensation.

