11 SAMPLE COLLECTION AND RETENTION

11.1 Collection

As outlined in Section 8.4 of this protocol, subjects in the treatment group will provide a blood sample for research purposes prior to beginning the FFF program, at 6 months and 12 months. Subjects in the control group will provide a blood sample for research purposes prior to the beginning the FFF program (6 months into the study) and again after 6 months in the program (12 months in the study). Processing will be completed in a Geisinger Laboratory and testing completed according to institutional policy.

[figure not shown]

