Geisinger Health piloted the FFF in Shamokin, PA, and plans to expand the program in the coming months, first in Scranton, PA and then in Lewistown, PA. The program faces capacity constraints such that the program cannot be offered to all eligible participants on the first day. We will carry out a pragmatic randomized controlled trial; eligible patients who are randomized to the treatment group will begin the FFF program immediately, while those randomized to the control group will begin the FFF program 6 months later. This will allow a rigorous examination of the effects of the program for outcomes 6 months after randomization (when the treatment group has been in the FFF program for 6 months and the control group has not yet started the FFF program).

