## 3.3. Secondary outcomes

### *6-month outcomes*

Secondary outcomes of interest include other biomarkers at 6 months: fasting glucose, weight, BMI, blood pressure, total cholesterol, LDL cholesterol, and triglycerides.

We will also examine outcomes based on self-reported survey data, including diet, exercise, and other healthy behaviors, self-efficacy, self-assessed physical and mental health, and patient satisfaction with Geisinger Health as a whole. We will also measure whether the patients have improved their understanding of diabetes and healthy eating.

Other outcomes help us understand the nature of the services offered. The control group has access to dietitian consultations and diabetes self-management classes as part of the standard of care, but we believe the take-up of such services will be higher among the treatment group. We ask about these consultations and classes in the patient surveys to verify that this is the case. We also survey participants about adherence to diabetes best preventive care and whether the subjects are signed up for SNAP benefits, as the program encourages take-up.

Using encounter data, we will also document the level of engagement with the program at the FFF clinic, including the number of weeks that the participants picked up food, the number of dietitian encounters, and the number of classes taken.

Health care utilization is another important secondary outcome. We will examine, at six months, the difference between the treatment and control group in: probability of any inpatient stay, any ED visit, any hospital visit (inpatient or ED). We will also examine the number of such visits, as well as the number of outpatient visits outside the FFF program. We will also examine medication usage, including insulin. Related, we will test for differences in paid claims both in those categories and in the amount paid among the Geisinger Health Plan beneficiaries and check that treatment and control are balanced on inclusion in this sample. We expect there may be outliers in payments, so we will estimate models in levels, logs, and check for differences in the distribution including the median. Any effect of the program on such outcomes may take time to materialize and thus may not be visible at 6 months.

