## Statistical Power and Sample Size Considerations

Using data for current (i.e. self-selected, non-randomized) FFF participants, we conducted parametric power calculations. These take into account the increase in power from controlling for baseline characteristics, but qualitatively similar results were found when we did not include

controls and when we used nonparametric (simulation) methods to estimate power. Similar results were also found when we based the calculations on similar patients in the counties where the two new sites (Lewistown and Scranton) will be located. All power calculations were conducted using STATA Version 15.

The table below shows that with the expected sample size of 500 we will have substantial power to detect small minimal detectable effects (MDE), as well as the ability to conduct heterogeneity analyses for the clinical outcomes. For utilization outcomes, we will have power to detect the (albeit) large reductions in utilization found in the observational literature.

Table 2: Statistical Power to Detect Targeted Minimal Detectable Effects (MDE)

					Required N for
	Mean	Std.Dev.	$\sqrt{1-R^2}$	Target MDE	MDE
Variable					
HbA1c after 180 days	8.58	1.74	0.66	10%	55
HbA1c after 365 days	8.56	1.67	0.66	10%	56
Weight after 180 days	228	64	0.96	10%	228
Weight after 365 days	228	64	0.96	10%	228
Hospital Visit (Inpatient or ED) 0-180 days	0.39	0.49	0.85	30%	397
Hospital Visit (Inpatient or ED) 0-365 days	0.48	0.50	0.87	30%	278
Hospital Visit (Inpatient or ED) 90-365 days	0.40	0.49	0.92	30%	447

We subsequently simulated statistical power for a model that estimates the effects of full engagement. For our primary outcome of HbA1c at 6 months, with power=80% and alpha=0.05 and planned sample size of 500, we can detect:

• Intent to treat effect of assignment to treatment: reduction of 3.7%

• IV treatment effect of full engagement: reduction of 5.2%

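### Weight, BMI and blood pressure are 6-month outcomes in the SAP, but Protocol 8.4 schedules them at month 6 in the treatment arm only

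*Protocol*

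**What the plan says.** Protocol 8.4 works with two lists. The shorter is laboratory work only and is tied to programme entry, at month 0 for treatment and about month 6 for control: "A set of blood tests (HbA1c, fasting glucose and lipid panel) will be collected for research immediately prior to the subject beginning the FFF program". The longer adds weight, BMI and blood pressure. For the treatment arm the longer set "will be collected at approximately the 6 and 12 month time points". For controls the longer set appears once: it "will be collected at approximately the 12 month time point (plus or minus 1 month) for the control group". Baseline values in both arms are taken from the medical record of the preceding year.

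Protocol 11.1 says controls "will provide a blood sample for research purposes prior to the beginning the FFF program (6 months into the study"), and again at 12 months.

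The SAP needs more than this at month 6. Section 3.3 states: "Secondary outcomes of interest include other biomarkers at 6 months: fasting glucose, weight, BMI, blood pressure, total cholesterol, LDL cholesterol, and triglycerides". Section 2 explains why month 6 is the key time, being the point "when the treatment group has been in the FFF program for 6 months and the control group has not yet started the FFF program". The power table, which is the same in both documents, has a row labelled "Weight after 180 days".

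**The concern.** Month 6 is the only planned time at which one arm has had the programme and the other has not. By month 12 controls have had about six months of it (SAP 3.3, 12-month outcomes), and Protocol 8.3.2 itself expects some convergence by then. A 12-month value therefore cannot stand in for a missing 6-month one.

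If 8.4 is followed exactly, treatment values are taken within a window of plus or minus 1 month. A control value exists only if a routine visit or an unscheduled check at programme entry recorded one. Such values would vary in timing and setting, might come from a selected subset, and some could be taken after entry. The asymmetry follows the arm, so randomisation gives no protection against it.

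Lower blood pressure is part of the primary hypothesis in Protocol 5.1, so the affected outcomes are not peripheral. HbA1c, fasting glucose and lipids do have a month-6 draw in both arms and are not affected.

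**Working it through.** **1. Schedule in Protocol 8.4, side by side**

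| | Treatment | Control |
|---|---|---|
| Month 0 | Blood tests | None scheduled |
| About month 6 | Blood tests, weight, BMI, blood pressure | Blood tests |
| About month 12 | Blood tests, weight, BMI, blood pressure | Blood tests, weight, BMI, blood pressure |

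Controls with a scheduled month-6 weight, BMI or blood pressure: 0 of about 250. The longer list is written out three times in 8.4 (baseline, treatment follow-up, control follow-up), so its absence from the control month-6 collection is a real difference in the text. The control events table is broken in the copy reviewed and the flow diagram is not shown; nothing here rests on either.

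**2. Reproducing the plan's figure for weight**

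Inputs from the power table: mean 228 (no unit given), SD 64, √(1−R²) = 0.96, target difference 10%. Power of 80% and alpha of 0.05 are stated for the primary outcome. I assume they apply to this row and that the test is two-sided, so the multiplier is 1.960 + 0.842 = 2.802.

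- Residual SD = 64 × 0.96 = 61.44
- Target difference = 0.10 × 228 = 22.8
- Total N = 4 × (2.802 × 61.44 / 22.8)² = 228

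This matches the stated 228. It is a two-arm calculation with 114 weights per arm, so it presupposes control weights at 180 days.

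**3. Power with incomplete control values**

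The documents give no coverage figure, so the shares below are assumptions. With 250 treatment values and n controls:

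SE = 61.44 × √(1/250 + 1/n); detectable difference = 2.802 × SE.

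| Control coverage | n | SE | Detectable difference | % of mean |
|---|---|---|---|---|
| 100% | 250 | 5.50 | 15.4 | 6.8% |
| 75% | 187.5 | 5.94 | 16.6 | 7.3% |
| 50% | 125 | 6.73 | 18.9 | 8.3% |
| 25% | 62.5 | 8.69 | 24.3 | 10.7% |

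Setting the detectable difference to 22.8 gives n of about 74, or about 30% coverage. Above that share the 10% target is still met.

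**4. Bias if the measured controls are selected**

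Let p be coverage and g the gap, in residual SDs, between controls with and without a value. Both are assumptions. Bias = (1 − p) × g × 61.44. With d = bias/SE and no true effect, the two-sided false-positive rate is Φ(−1.96 − d) + 1 − Φ(1.96 − d).

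For g = 0.2:

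| p | Bias | % of mean | d | False-positive rate |
|---|---|---|---|---|
| 75% | 3.1 | 1.3% | 0.52 | about 8% |
| 50% | 6.1 | 2.7% | 0.91 | about 15% |
| 25% | 9.2 | 4.0% | 1.06 | about 19% |

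At the same three coverages, g = 0.1 gives 5.8%, 7.4% and 8.3%, and g = 0.3 gives 12.1%, 27.8% and 35.6%.

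**The case against.** The strongest counter-text is SAP 3.1. It describes study subjects going to a laboratory for the blood test and then says weight, BMI and blood pressure are recorded too, without restricting this to an arm. Since controls have a blood test at about month 6, one could read the measures as accompanying it. Protocol 8.2.1 says data from the controls' first six months will serve as control data, and Protocol 5.2 promises clinical measures from both groups. Together these show an intention to have control values, and nothing suggests a deliberate decision to leave controls unmeasured.

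That intention is not a schedule. SAP 3.1 gives no time point, 8.2.1 lists no measures, and 5.2 defers to visits described later, which are those in 8.4. The regular tracking in SAP section 2 concerns programme participants, which controls are not before entry, and the interval stated in the Protocol's rationale covers only HbA1c and lipids. For people who leave the programme but stay in the study, 8.4 says "the lab work will be covered by the research study and the surveys will be completed by phone or e-mail"; weight and blood pressure are not mentioned.

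Three points on the other side do stand:

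- Section 11.1 is weak support, because it speaks of blood samples in both arms at every time.
- The treatment events table has no row for these measures either, although 8.4 schedules them for that arm, so absence from the table proves nothing.
- The bias figures depend on coverage and gap values with no source in the documents. The gap must also persist after adjustment for the baseline value; 0.2 residual SD is about 12 weight units. They illustrate scale and are not estimates.

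The planned bounding analyses (Protocol 9.1.1, SAP 4) address differential loss from the study, not a measurement scheduled in one arm only. The SAP's balance check on missing values concerns baseline values.

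**Conclusion.** The concern holds on the wording of Protocol 8.4 alone. As written, the 6-month comparisons of weight, BMI and blood pressure in SAP 3.3 have scheduled data in one arm only, and this should be fixed.

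The scheduling gap needs no assumption. Its consequences do, because coverage of control values and the selection gap are unknown. Loss of power is minor unless fewer than about 30% of controls have a value. Selection matters more: over the assumed ranges the false-positive rate for weight runs from about 6% to 36%. No calculation was made for BMI or blood pressure, for which the documents give no SD. Only secondary outcomes are affected.

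**What to change.** In Protocol 8.4, add weight, BMI and blood pressure to the control month-6 assessment, taken before programme entry, so that both arms have the same set. Add a row for these measures to both arms' events tables, and align SAP 3.1 with the result.

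While amending, it would help to say outright what is now mostly implied: the control month-6 assessment has the same window of plus or minus 1 month, counted from randomisation, and is obtained whether or not the control starts the programme.

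The cost is a protocol amendment and, in my judgement, a few minutes per control. Controls who start are already contacted at 5 months to book and complete the baseline survey on site, so they need no extra visit. Controls who do not start would need the measures taken at a clinic or laboratory visit; the documents do not say how many there would be. The step has to come before entry, because a pre-programme value that is missed cannot be recovered afterwards.

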The coefficient β_1 measures intent-to-treat: the causal effect of being randomized into the treatment group. This can differ from the effect of the program if there is non-compliance: some subjects in the treatment group may decide not to join the program or join for a very short time. At the initial pilot site, 17% of those who begin the program are no longer in the program at 6 months. We plan to record outcomes for all subjects regardless of program participation and will estimate the equation using Two Stage Least Squares (2SLS), with the initial treatment assignment used as an instrumental variable for ultimate assignment. The 2SLS estimate measures the average causal effect of the program for those who choose to remain in it as a complementary parameter to the intent-to-treat analysis. In addition, if there is differential attrition from the study across treatment and control groups—despite our efforts to obtain outcomes from each subject including obtaining multiple forms of contact information for subjects and their family members and compensation for subjects' time, we will explore bounding estimates under a range of assumptions about effect sizes for those not observed.

For survey responses, we will consider answers in the top and bottom categories as separate outcomes and will test robustness to using nonlinear estimators. For patient satisfaction, we will calculate the net promoter score as an outcome as well. To avoid concerns about multiple hypothesis testing, each category of questions will be compiled into an index and we will report p-values corrected for the multiple tests when presenting results for each question individually.

In addition to outcome comparisons across all of the participants, we will consider heterogeneous treatment effects in three ways. First, a priori we are interested in whether the program is

CONFIDENTIAL AND PROPRIETARY

[figure not shown]

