Recruitment will be conducted over the phone; the program will be described, consent will be sought, and then patients will be randomized to either treatment ("start FFF now") or control ("start FFF later"). Note that all patients eligible for FFF, whether or not they agree to participate in the study, will be randomized to determine the timing with which they will enroll in FFF. This is the way the program is being introduced, akin to a lottery, and ensures that there is no incentive to refuse to participate in the study in order to start FFF sooner. Recruitment staff will discover whether the patient is randomized to start now or start later in a tamper proof REDCap application, which consults a randomized allocation table that the recruiter cannot access and a treatment status that is locked along with the patient's identifying information and study ID. The recruiter will then set up the patient's first appointment for those in the treatment group and will reach out to patients 5 months later to set up appointments for the group randomized to start later. We anticipate finding the patients 5 months later because all subjects are Geisinger Health patients, whose current address is on file, and we will ask for two other contacts at the time of recruitment.

The randomization is stratified using levels of HbA1c: <8.0 (in the event that the threshold is lowered),  $\geq$ 8.0 and <9.5, and  $\geq$  9.5 to attempt to ensure balance on a key pre-study control and because we are interested in estimating effects separately by these categories to inform

threshold setting in future applications. The randomization happens separately by location (Scranton and Lewistown) as well.

The trial will launch in April 2019 in Scranton, and likely June 2019 in Lewistown. We plan to continue enrollment until we attain at least 500 subjects (half in treatment) or when the recruitment period has lasted 2 years. If recruitment slows, we will consider lowering the eligibility threshold to an HbA1c of at least 7.5 rather than 8.0, and we may consider expanding the geographic limit.

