# 4. Empirical Model

Our initial analysis will estimate intent-to-treat models using linear regression. Consider an outcome,  $Y_i$ , such as HbA1c, for each subject i. The primary specification is:

$$Y_i = \beta_0 + \beta_1 1(\text{Treatment})_i + \beta_2 X_i + \varepsilon_i$$

For our analysis,  $1(\text{Treatment})_i$  is an indicator equal to one if the subject was randomized to the treatment group and zero if the subject was randomized to the control group;  $X_i$  is a vector of control variables. These control variables should be uncorrelated with the treatment indicator, but they can aid in the precision of the estimate because they are correlated with the outcome Y. First, we will include strata indicators for location and HbA1c category. We will also include the lag of the dependent variable, which substantially improves power: for clinical test results that would be the most recent test result prior to enrollment in the study. For utilization outcomes such as inpatient visits, we will include the number of such episodes observed in the 12 months prior to study enrollment.

We also plan to include standard demographic controls: age (5-year age bins), sex (indicator that the patient is male), race/ethnicity (indicators for African American and Hispanic). For the clinical test results, we will also include a control for the number of days from the baseline measure to the follow-up test in order to improve precision. If this number of days is not balanced across treatment and control, we will control for the number of days between the baseline test and the date of enrollment into the study. We will also include the month-year of entry into the study unless this measure is highly correlated with the number of days between blood tests and reduces statistical precision.

We will also estimate models where the outcome is the difference between the baseline and the follow-up exam instead of including the baseline exam result as a control:

$$\Delta Y_i = \beta_0 + \beta_1 1 (\text{Treatment})_i + \beta_2 X_i + \varepsilon_i$$

This is a more restrictive model but may improve statistical precision and requires fewer controls. For models that control for lagged values or in this difference model, we will estimate models for those with non-missing values. We will also test whether missing lagged value is balanced across treatment and control for each measure. Note that all patients have a baseline HbA1c that was used in recruitment.

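### The control arm's month-6 HbA1c, the primary endpoint, is tied to program start, with no window and no procedure for controls who start late or never start

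*Protocol*

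**What the plan says.** The primary endpoint is HbA1c at 6 months (Protocol 8.5; SAP 3.2 counts this from entry into the trial). The two arms reach it by different routes.

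- **Treatment arm.** Protocol 8.4 has research measurements "collected at approximately the 6 and 12 month time points (plus or minus" 1 month). No program event is required.
- **Control arm.** The parallel sentence in 8.4 gives controls only the month-12 measurement, at the 12 "month time point (plus or minus 1 month) for the control group". Their one research draw near month 6 is the pre-program sample, "collected for research immediately prior to the subject beginning the FFF program", placed at "approximately month 6 for the control group". No window is attached. Protocol 11.1 repeats the link: controls give a "blood sample for research purposes prior to the beginning the FFF program (6 months into the study").
- **Start dates.** Footnotes to the tables in Protocol 8.4.1 put the treatment start within 1 month of consent. The control start is about 6 months after consent, with no upper limit.
- **Recall of controls.** Under Enrollment & Randomization in the SAP, the recruiter "will reach out to patients 5 months later to set up appointments for the group randomized to start later". A month-6 lab visit separate from program entry is not described.
- **General aim.** Protocol 9.1.1: "We plan to record outcomes for all subjects regardless of program participation".
- **Timing covariate.** SAP section 4 adjusts clinical results for days from baseline test to follow-up test, then adds: "If this number of days is not balanced across treatment and control, we will control for the number of days between the baseline test" and enrollment.

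**The concern.** In the treatment arm the start-triggered sample is only a month-0 value, and every subject already has a baseline HbA1c from recruitment (SAP section 4), so losing it does little harm. In the control arm the same trigger produces the primary endpoint.

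The SAP expects that some subjects assigned to treatment may decide not to join. Randomization implies similar people among the controls. In the treatment arm such a person still has a time-based 6-month draw. In the control arm that person never reaches the event that triggers the draw, and someone who keeps postponing is drawn late. If the text is followed as written, the intent-to-treat contrast would compare a treatment arm measured regardless of uptake with a control arm measured according to uptake. A value that was never drawn cannot be recovered in the analysis.

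**Working it through.** **1. The safeguards, set against a control who never starts or starts late**

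- The aim in Protocol 9.1.1 covers this person in principle but gives no date, window or procedure.
- The sentence in Protocol 8.4 that pays for lab work covers people who leave the program and stay in the study. It does not mention someone who never entered it, in either arm.
- Bounding (Protocol 9.1.1, SAP section 4) is exploratory and is triggered by differential attrition. It does not address late draws, and equal rates of missingness could still hide different kinds of missing people.
- The fallback covariate in SAP section 4 ends at enrollment, so it carries no information on when the follow-up test was done.

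**2. The plan's own yardstick**

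The SAP states a detectable intent-to-treat effect of 3.7% with N = 500, 80% power and alpha 0.05. Its Table 2 gives mean 8.58, SD 1.74 and √(1−R²) 0.66 for HbA1c at 180 days.

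- Stated effect in points: 0.037 × 8.58 = 0.317.
- Closed-form check with 250 per arm, two-sided: (1.960 + 0.842) × 1.74 × 0.66 × √(2/250) = 0.288 points, or 3.35%. This does not reproduce 3.7%, which would need √(1−R²) of about 0.73. The SAP says its figure was simulated, so I do not call it wrong. I use 0.317 as the yardstick.

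**3. Can the share of never-starters be derived?**

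With one instrument, the detectable 2SLS effect is roughly the intent-to-treat effect divided by mean engagement, so 3.7/5.2 = 0.71 suggests the engagement assumed in the simulation. Take two facts from the documents: a treatment start up to 1 month after consent (5/6 = 0.833 of six months) and 17% of pilot starters gone by month 6.

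- All leavers go at once: 0.833 × 0.83 = 0.69.
- Leavers go evenly over time: 0.833 × 0.915 = 0.76.

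The value 0.71 lies inside this range with no never-starters at all. The share cannot be derived.

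**4. Illustration of bias (both inputs assumed)**

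Let a share m of controls be unmeasured, with adjusted mean HbA1c differing by D from those measured. The observed control mean is then off by m × D.

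| m | D = 0.5 | D = 1.0 |
|---|---|---|
| 5% | 0.025 (8% of 0.317) | 0.05 (16%) |
| 10% | 0.05 (16%) | 0.10 (32%) |
| 20% | 0.10 (32%) | 0.20 (63%) |

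The residual SD from Table 2 is 1.74 × 0.66 = 1.15, so these values of D are 0.44 to 0.87 residual SDs.

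**5. Precision**

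The SD that makes 3.7% detectable with 250 per arm is 1.267. The detectable effect is then 2.802 × 1.267 × √(1/250 + 1/n), with n the measured controls. For n = 237.5 (5% missing) it is 3.75% of the mean, and for n = 200 (20% missing) it is 3.92%. Power at 3.7% falls from 80% to 79% and 75%. The loss is small; bias is the issue.

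**The case against.** A reader might infer that controls have no scheduled primary endpoint at all. The documents do not support that. Protocol 8.4 and 11.1 both name month 6, and the control events table in 8.4.1 shows two research-lab marks, probably at months 6 and 12, although the column positions are lost in the text available. SAP 3.1 says blood is drawn at a Geisinger lab; in Protocol 8.4 it is the survey that is completed at the program clinic. So the draw is not shown to be part of the first program visit. The month-5 contact sets up appointments without limiting them to program visits, and two further contacts are collected for each subject.

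A reader might also divide 0.71 by 0.83 or 0.915 and conclude that 14% to 22% never start. That leaves out the permitted start delay (step 3). The SAP also expects low refusal and dropout, and a never-starter is not necessarily an undrawn control.

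Other points stand in part. The treatment clock may itself run from program start, so calling that arm's draw calendar-based is only safe in the sense that no program event triggers it. A late control draw is still taken before the program and adds only drift, whose size I cannot estimate. Dropping a post-randomization timing covariate when it differs by arm is defensible, and the protocol's own model keeps it without that switch. Interim HbA1c values in the health record (Protocol 8.6) might fill some gaps.

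None of this supplies a window, or a procedure for a control who starts late or never does.

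**Conclusion.** The point holds in limited form. The control draw is nominally at month 6 but defined by program start, with no window and no provision if the start is late or does not happen; the treatment draw has a window and no such condition. Measurement of the primary endpoint can therefore depend on post-randomization uptake in one arm.

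The size is unknown. A shift of 0.025 to 0.20 points, 8% to 63% of the stated detectable effect, rests on assumed values for both the share unmeasured and the adjusted difference. If unmeasured controls have higher HbA1c, the observed control mean is too low and benefit is understated; if lower, benefit is overstated. If nearly all controls are drawn on time, the effect is negligible. It would go too far to say that the comparison becomes treatment subjects against controls who start: that requires every non-starter to go unmeasured, contrary to the stated aim. I rate this as a cheap improvement worth making.

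**What to change.** - In Protocol 8.4, 8.4.1 and 11.1, schedule the month-6 research lab in both arms at 6 months after randomization, plus or minus 1 month. For controls, place it before program start but do not make it conditional on one.
- Have the month-5 contact book that lab visit for every control, including those who decline or postpone the program.
- Extend the lab-coverage sentence in 8.4 to subjects in either arm who never begin the program.
- Report the share drawn in window by arm.

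The cost is protocol wording and a change to the month-5 contact. The draw, the study-paid lab and the $50 gift card are already planned. The downside is that some controls make a lab trip separate from their first program visit.
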